4.1.1.1.2 Secondary Safety Endpoint

The secondary safety endpoint is the tabulation of all AEs (both device related AEs used in the primary safety endpoint and all other AEs) for the overall AE rate to establish a safety profile for use of the

Medtronic Business Restricted

Novapak device. All AEs will be collected for each subject from time of treatment until their study completion. Study completion for each subject is the time-point at which the 30-day follow-up visit is completed, outstanding AE follow-up (if any) has been concluded, and a Study Exit CRF has been completed. For subjects who withdrew or were lost to follow-up, study completion will be the date of withdrawal or the date the subject meets the definition of lost to follow-up. Refer to **Section 13** for how missing data will be handled.

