8.1 Study Population

A sample size was selected that is adequate to assess the safety and treatment effectiveness of the Medtronic Novapak Nasal Sinus Packing and Stent device. The sample size is not based on a formal power calculation; however, results from no fewer than 75 subjects and one device used per subject are expected to provide sufficient evidence that the Medtronic Novapak does not introduce new complications or increase severity or likelihood of occurrence of existing complications in this population. It is anticipated that there may be subjects who will not receive nasal packing for any reason after enrollment (including withdrawal prior to treatment). Based on literature, it is expected that an average of one sinus per subject will be treated. Thus, if all 75 subjects have one sinus treated, data will be collected for approximately 75 sinuses. Note: all sinuses requiring treatment will be treated, 75 sinuses are the minimum number required for the protocol, but additional sinus data is likely.

In relationship to this unilateral or bilateral treatment, the number of devices used could be one or two per subject. Therefore, total product used in this study would be a minimum of 70 if a single device is used, to approximately 150 if two devices are used per subject. Note: Physicians are free to modify the size and shape of the device to fit in a unique individual anatomy.

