- Potential toxicity reactions – components of the packing could lead to a toxicity reaction due to a non-biocompatibility reaction occurring, but the reaction would not be expected to go beyond an inflammatory response. (i.e., redness, swelling, etc.)
- Potential allergic hypersensitivity reactions – components of the packing could lead to an allergic hypersensitivity reaction - A patient may experience edema and difficulty breathing with IV medications used as medical intervention.
- Foreign Body Reaction - Potential tissue interactions with packing components, fragments, or surface texture. In addition to an inflammatory response, it usually includes the formation of a foreign body granuloma, or encapsulation around a foreign object. Medical intervention may be taken to remove the product.
- Inflammation - This harm includes local irritation from the product. This risk may require Oral medication to reduce inflammatory response.
- Fever - A medium-low grade fever may develop. This risk may require Oral medication to reduce inflammatory response.
- Device Fragments in Patient – If a device fragments migration of pieces of the stent could result in possible medical intervention needed
- Pain – during post-operative removal of non-dissolving packing devices most patients have reported some mild temporary pain.
- Decreased Therapeutic Response – The packing may not perform as expected and not control the risks as intended. It would not result in surgical correction but may require a minor medical intervention.

The use of the Novapak Nasal Sinus Packing and Stent may involve the risks listed above for all packing type devices, with the exception of pain upon removal, since it dissolves away with irrigation. There may be other discomforts and risks related to the Novapak Nasal Sinus Packing and Stent device and/or this study that are not foreseen at this time.

Medtronic Business Restricted

These are the current risks of Novapak seen in the field based on reports to our complaint system: (number of reported events as of June 24, 2022)

- Irritation – potential shellfish hypersensitivity (1)
- Post-operative bleeding requiring secondary controls (3)
- Post-operative device migration to oral cavity (1)
- Post-operative edema and pain (2)

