11.5 Reporting of Adverse Events

11.5.1 Adverse Event and Device Deficiency Classification

All AE and DD will be reviewed by a Medtronic representative. AEs will be classified according to the definitions provided.

Upon receipt of AE at Medtronic, a Medtronic representative will review the AE/DD for completeness and accuracy and when necessary, will request clarification and/or additional information from the Investigator. Medtronic will utilize Medical Dictionary for Regulatory Activities (MedDRA), to assign a MedDRA term for each AE based on the information provided by the investigator.

Regulatory reporting of AEs and DDs will be completed according to local regulatory requirements. Refer to **Table 11** for a list of required investigator and Medtronic reporting requirements and timeframes. It is the responsibility of both to abide by any additional AE reporting requirements stipulated by the IRB/REB responsible for oversight of the study.

Medtronic Business Restricted

Appendix A contains the FAL, which is a list of AEs related to the device or procedure that have been observed in previous studies and may be experienced by subjects. This list may help to assess if an AE is unanticipated in nature.

For emergency contact regarding a SAE and/or SADE, contact a study representative immediately (refer to the study contact list provided in the study site's study documents binder/investigator site file or refer to the Sponsor contact information provided on the title page).

AEs will be classified according to the standard definitions as outlined below:

Table 10: Adverse Event Classification Responsibilities

What is classified?	Who classifies?	Classification Parameters
Relatedness	Investigator	Device and/or Procedure. 
Relationship: not related, possible, probable, causal
	Sponsor	Device and/or Procedure. 
Relationship: not related, possible, probable, causal
Seriousness	Investigator	SAE, DD with SADE potential
	Sponsor	SAE, DD with SADE potential
Diagnosis	Investigator	Based on presenting signs and symptoms and other supporting data
	Sponsor	MedDRA term assigned based on the data provided by Investigator

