### 3. Introduction

Medtronic, Inc. is sponsoring the Novapak Nasal Sinus Packing and Stent Study, a prospective, observational, multi-site, non-controlled, non-randomized, case-series, investigational, clinical study. The purpose of this study is to assess the safety of the Novapak Nasal Sinus Packing and Stent device used as indicated post-operatively in patients undergoing nasal/sinus surgery. In addition, this study will observe some key measures of device effectiveness from the physician and subject perspective.

The Novapak Nasal Sinus Packing and Stent study is being conducted as a non-significant risk postmarket investigational study in the US and Canada in accordance with Canadian local regulations and International Organization for Standardization (ISO) 14155:2020 in support of European Medical Device Regulation (EU MDR) regulatory submission for a Conformité Européene (CE) Mark.

The Novapak prospective observational clinical trial clinical investigation plan (CIP) provides the guidelines for this statistical analysis plan (SAP). The purpose of this SAP is to provide details for Novapak therapy-specific data analyses. Reports generated using study data may not contain all the analyses described below; however, if a report contains an objective outlined within this document, the analysis of that objective will be performed as described in this SAP. If additional analyses are required but not covered in this SAP, a separate SAP addendum may be needed.

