## 7.9 Evaluation of Objectives

### 7.9.1 Safety objective assessment

The safety objective is evaluated by:

- The number of Adverse Events that are directly attributed to the device and/or those that cannot be determined.
- The number of Adverse Events.

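### SAP 7.9.1 plans the primary safety result as two raw adverse-event counts, without the rate and confidence interval the protocol requires and without any result by seriousness or event type

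*SAP*

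**What the plan says.** SAP 7.9.1 lists two measures for the safety objective. The first is "The number of Adverse Events that are directly attributed to the device and/or those that cannot be determined". The second is "The number of Adverse Events" with no qualifier. The list is closed, whereas the lists in SAP 7.6 and 7.7 are expressly left open to additions. SAP section 3 gives the text its force: "if a report contains an objective outlined within this document, the analysis of that objective will be performed as described in this SAP". No other SAP section plans an AE analysis, and seriousness, MedDRA coding and expectedness are not mentioned anywhere in the SAP.

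The protocol asks for more:

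- Section 4.1.1.1.1 calls for a point estimate of the rate, with a confidence interval, for AEs attributable to the device or of undetermined cause.
- Section 4.1.1.1.2 calls for a table of all AEs "for the overall AE rate to establish a safety profile for use of the" device.
- The safety row of the synopsis asks that device-related AEs be characterized.

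The protocol also supplies the variables. Under section 11.5.1 the sponsor uses MedDRA "to assign a MedDRA term for each AE based on the information provided by the investigator". In Table 10 both the investigator and the sponsor classify relatedness and seriousness. Appendix A lists foreseeable events to help recognise unanticipated ones.

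**The concern.** The primary objective in both documents is a safety profile. A profile says what happened, how serious it was and in how many subjects. A count of events says none of this, and it is not a rate. Someone who programs SAP 7.9.1 as written, and validates it at the level that SAP section 8 reserves for the primary objective, will produce two integers.

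The study supports a CE Mark submission, Appendix A states that the device has had no previous clinical study, and protocol section 12 provides neither a clinical events committee nor a data monitoring committee. The pre-specified safety tables therefore carry much of the weight. If they are not written down, which breakdown is shown, and on which denominator, will be settled after the data are seen.

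**Working it through.** There is no stated power, event rate or safety threshold to reproduce, so the check has two parts: a comparison of texts, then arithmetic to show what a bare count leaves out.

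**1. Required against planned**

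| Element | Protocol | SAP 7.9.1 |
|---|---|---|
| Rate with a denominator | 4.1.1.1.1 and 4.1.1.1.2 | absent |
| Confidence interval | 4.1.1.1.1 and synopsis | absent |
| Table of all AEs | 4.1.1.1.2 | a total only |
| Characterization of device-related AEs | synopsis | a total only |
| Relatedness | Table 10 | used in the first count |
| Seriousness | collected, Table 10 | not used |
| MedDRA term | assigned, 11.5.1 | not used |

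The protocol does not itself require a breakdown by term or seriousness. It requires a profile and a characterization, and those two variables are the obvious means of giving them. Nor does the protocol fill the gap elsewhere: 4.1.1.1.1 refers to designated endpoint AEs in section 11.4, but 11.4 does not define them.

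**2. What a count leaves out**

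Inputs: n = 75, the planned minimum (SAP section 6); exact Clopper-Pearson limits; 95% two-sided level (assumed); event numbers (assumed, for illustration). For x subjects with an event, the lower limit is the 0.025 quantile of Beta(x, n − x + 1) and the upper limit is the 0.975 quantile of Beta(x + 1, n − x). For x = 0 the lower limit is 0 and the upper limit is 1 − 0.025^(1/75) = 4.8%.

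| Subjects with the event | Rate | Exact 95% CI |
|---|---|---|
| 0/75 | 0% | 0 to 4.8% |
| 1/75 | 1.3% | 0.03 to 7.2% |
| 3/75 | 4.0% | 0.8 to 11.2% |
| 7/75 | 9.3% | 3.8 to 18.3% |

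*Events against subjects.* Take 7 device-attributed AEs. They could come from one subject or from seven, so the subject-level rate could be anything from 1.3% to 9.3%. The SAP result is 7 in each case.

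*Type of event.* Protocol 10.1 lists four kinds of field complaint, with 1 + 3 + 1 + 2 = 7 reports. Seven device-attributed events can be divided over four kinds in C(7 + 3, 3) = 120 ways. With the other AEs held fixed, both SAP totals are identical for all 120, from seven irritations to seven bleeds needing secondary control.

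*What the study could show.* The chance of seeing at least one case of a complication with true rate p is 1 − (1 − p)^75. For assumed rates of 1%, 2%, 3% and 5% this is 53%, 78%, 90% and 98%. Such a case would probably be recorded, coded and classified, but the two planned counts would not identify it.

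**The case against.** The strongest reply is that the SAP takes its guidelines from the protocol, and the protocol already plans the rate, the interval and the table. SAP 7.2 summarizes categorical variables by frequency and percentage, and seriousness and MedDRA term are categorical. SAP section 3 also foresees an addendum for analyses not covered. This stands as far as it goes: fuller tables are unspecified, not excluded. It does not show that the SAP commits to them. Section 7.9.1 is the text that governs this objective, and the generic rule names no AE variable.

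Several stronger readings are tempting, and the documents do not support them:

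- *Known harms and new complications would be invisible.* The protocol plans a table of all AEs and a characterization of device-related ones. What can be said is that the SAP's planned result does not require them to be shown.
- *A serious device effect counts the same as a mild headache.* By the definitions in protocol 11.4, a SADE is a device effect and so falls in the first count. A headache judged unrelated to the device does not. The two are indistinguishable only if the headache is also device-related or of undetermined cause.
- *A cluster of serious device events would hardly move the result.* That looks only at the all-AE count. Device-attributed events also raise the first count, where the same number could be a large change.
- *The SAP fails to test the claim in protocol 8.1.* The statement that the device "does not introduce new complications or increase severity or likelihood of occurrence of existing complications in this population" explains the choice of 75 subjects. It is not an objective or a planned test in either document.
- *Hypersensitivity should be split by the shellfish-screening answers.* The schedule (Table 4) lists those questions as a procedure and not under data collection. Section 9.4 requires only the reason for non-eligibility to be recorded. It is not shown that enrolled subjects' answers will be available.

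**Conclusion.** The point holds as a gap in specification. As written, the SAP's planned safety result does not deliver the rate with confidence interval that protocol 4.1.1.1.1 requires. It also does not deliver the table and characterization needed for the safety profile. The data will be collected, so this is a correctable omission and not a flaw in the design. It should be corrected before analysis.

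In the illustration, one event count is compatible with subject-level rates from 1.3% to 9.3%. The event numbers and the 95% level are assumptions. So is n = 75 as the denominator, because protocol 8.1 expects that some enrolled subjects may not receive packing, while the SAP 7.1.3 analysis set contains only those who do. With 70 treated, for example, the upper limit for zero events would be 5.1% instead of 4.8%.

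**What to change.** Replace the two bullets in SAP 7.9.1 with one table specification. Give the number and percentage of treated subjects with at least one event, with an exact 95% confidence interval, and the number of events. Do this for (a) all AEs, (b) AEs device-related or of undetermined cause, (c) SAEs and (d) SADEs, each tabulated by MedDRA term. State the confidence level, since neither document does. State also which Table 10 relatedness categories form row (b), and whether the investigator's or the sponsor's classification is used.

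Two optional additions:

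- An individual listing of device-related AEs judged unanticipated. This judgement should use Appendix A together with the other sources it names. Its entries are broad, so a simple on-list or off-list flag could hide an unusual event within a general category.
- Rows for the field-reported harm types in protocol 10.1. No document designates these as endpoints, so this is a choice of presentation.

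The cost is SAP wording and a few standard AE tables from data already collected. No visit, procedure or clinical rule changes. The small drawback is that many rows will hold zero or one event with wide intervals.

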### 7.9.2 Effectiveness objective assessment

The effectiveness objective is evaluated by:

• The number of adhesions from procedure through 1-month post treatment.

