4.1.1.1.1 Primary Device Safety Endpoints

The primary safety endpoint is an assessment of all AEs that are directly attributable to the device and/or for which cause cannot be determined, and that meet the definition of designated primary safety endpoint AEs (see section 11.4) that will be used to determine the point estimate and its confidence interval. This endpoint will be analyzed by calculating the point estimate with a confidence interval of its rate. All AEs will be collected for each subject from time of treatment until their study completion.

Study completion for each subject is the time point at which the 30-day follow-up visit is completed, outstanding AE follow-up (if any) has been concluded, and a Study Exit CRF has been completed. For subjects who withdrew or were lost to follow-up, study completion will be the date of withdrawal or the date the subject meets the definition of lost to follow-up. Refer to **Section 13** for how missing data will be handled.

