10.1 Potential Risks

Medtronic follows rigorous Quality Assurance and Control procedures throughout the life of a product, from the business analysis phase through development, market release, and post-market surveillance. The risk analysis process for the Novapak Study, is being performed in accordance with ISO 14971 and will ensure that the level of risk is acceptable prior to starting the study.

There are no incremental risks introduced to the subject as a result of participation in this study.

There are inherent risks for nasal sinus surgery as well as any surgery where removal, cutting and modification of tissues are required. These risks include:

- Mild Bleeding
- Adhesions, tissue synechia
- Fatigue
- Infection
- Moderate Pain
- Inflammation and swelling
- Nasal Congestion
- Mild to moderate headaches
- Facial pressure

Nasal sinus packing in general has tried to address these surgical complications but may result in risks that are specific to the use of packing, as follows:

- Bleeding – present if packing is inadequate or bleeding is excessive– may require post-operative controls (e.g., suturing, cautery, more packing)
- Adhesions – present if packing is inadequate to separate tissue compromised due to surgical trauma – requires post-operative debridement of tissues which may lead to bleeding.
- Scarring - This risk is where the tissue heals abnormally

- Infection – due to introduction of bacterial during the surgery and/or if sterility is breached - packing could encourage bacterial growth if design controls are not in place to control bacterial growth.
- Toxic Shock Syndrome –defined as “A severe illness caused by infection with staphylococcus aureus and characterized by high fever of sudden onset, vomiting, diarrhea, and myalgia, followed by hypotension and in severe cases, shock; a sunburn like rash with peeling of the skin, especially of the palms and soles, occurs during the acute phase.”
- Respiratory Obstruction – physical obstruction of the breathing pathway – This harm may occur from stent migration and cause difficulty breathing (i.e., hypoxia, dyspnea)
- Aspiration of the packing – causes respiratory obstruction with tachypnea can lead to aspiration pneumonia, urgent medical intervention may be necessary
- Pneumonia - If the stent were aspirated, pneumonia may occur. The patient may be treated with IV medication.

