11.1 Adverse Events

AE definitions are provided in **Table 9**. All AE information will be collected throughout the study duration, starting during sinus surgical procedure and treatment with the Novapak device and concluding with the 30-day visit and/or study exit (whichever occurs first).

Reporting of these events to Medtronic will occur on an AE eCRF. Each event must be reported separately. Documented pre-existing conditions are not considered AEs unless the nature or severity of the condition has worsened.

In all geographies, UAEs occurring post-surgery need not be reported unless the adverse event worsens or is present outside the stated timeframe post-surgery.

Table 8: Post-Surgery Unavoidable Adverse Events

Event Description	Timeframe – days after surgical procedure
Sudden visual changes or ocular swelling	1
Fever higher than 101°F	1
Anesthesia related complications	2
Medication related complications	2
Mild bleeding (bloody discharge)	5
Constant clear watery discharge	7
Facial pressure	7
Fatigue	7
Inflammation and swelling	7

Medtronic Business Restricted

Mild to moderate headaches	7
Moderate pain	7
Numbness of the Teeth or Palate	7
Nasal congestion	10

For AEs that require immediate reporting (see **Table 11**), initial reporting may be done by email or phone, or on the eCRF completing as much information as possible. The completed AE eCRF must be submitted to Medtronic as soon as possible.

Any medication/treatment associated with the treatment of an AE must be reported.

Subject deaths are also required to be reported. Refer to Section 11.6 for Subject Death collection and reporting requirements.

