Appendix A – Foreseeable AE List

The information provided in this section pertains to foreseeable adverse events that may be observed in the Novapak Study and may collectively assist in identifying those events for a given device or therapy that are unexpected in nature. The foreseeable adverse events information consists of three parts: 1) observed adverse device effect(s) in similar Medtronic studies, 2) adverse events reported in published literature, and 3) additional foreseeable adverse events. An evaluation of potentially anticipated events, adverse device effects observed in previous clinical studies, and reported events in literature may be used in combination with device labeling, current event reporting information, and other published data to assess for an unexpected occurrence.

The use of Novapak Nasal Sinus Packing and Stent device involves application after surgery, therefore, standard adverse events associated with a surgical procedure may be experienced (e.g. anesthesia complications, injury, infections, bleeding, exacerbation of pre-existing conditions, healing

Medtronic Business Restricted

complications, etc.). However, the focus of this section is to address in more detail, those events that are foreseeable due to the use, performance, and/or presence of the device under investigation.

Potential risks associated with the use of the Novapak Nasal Sinus Packing and Stent device, as well as risk minimization are discussed within Section 10. Treatment required for procedure and/or device related adverse events may include medication, device removal, or other surgical and medical remedies.

The remainder of this section provides examples of adverse event data from previous Medtronic clinical studies and literature. Evaluation of potentially anticipated events may involve data in this section as well as a thorough review of all available information (e.g. labeling, current event reporting, published data, etc.).

Risks and Complications of Sinus Surgery

Normal Expected Complications

- mild bleeding
- inflammation and swelling
- nasal congestion
- moderate pain
- fatigue
- mild to moderate headaches
- facial pressure

Complications that may occur

- Bleeding / Hemorrhaging
- Adhesions of Tissues
- Scaring of Tissues
- Infections
- Nasal Crusting or Dryness
- Loss of Smell or Taste
- Cerebral Spinal Fluid Leak
- Empty Nose Syndrome
- Damage to the Ocular Orbit
- Numbness of the Teeth or Palate
- Septal Perforation

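### Does the plan leave open whether an adhesion scored for effectiveness also counts as a device adverse event?

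*SAP*

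**What the plan says.** **Effectiveness.** Protocol section 9.9 has the physician score adhesions, and debride them if necessary, at Day 14 and Day 30. SAP section 7.9.2 then evaluates "The number of adhesions from procedure through 1-month post treatment", together with an ordinal grade from 0 to 3.

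**Safety.** SAP section 7.9.1 evaluates "The number of Adverse Events that are directly attributed to the device and/or those that cannot be determined", and separately the number of all adverse events. It names no event type, so it neither includes nor excludes adhesions. Protocol section 4.1.1.1.1 describes the primary endpoint more narrowly, as events "that meet the definition of designated primary safety endpoint AEs (see section 11.4"). Section 11.4 contains no such definition.

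**Adhesions as a risk.** Protocol section 10.1 lists "Adhesions, tissue synechia" among the inherent risks of sinus surgery. It lists adhesions again among the risks specific to packing, as "present if packing is inadequate to separate tissue compromised due to surgical trauma". Appendix A repeats the packing entry and puts "Adhesions of Tissues" among the surgical complications that may occur. Section 11.5.1 describes Appendix A as the foreseeable event list, "which is a list of AEs related to the device or procedure".

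**What need not be reported.** Section 11.1 says that "UAEs occurring post-surgery need not be reported unless the adverse event worsens or is present outside the stated timeframe post-surgery". Table 8 gives the events and their time limits, and adhesions are not among them.

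**The concern.** The same finding on endoscopy has two possible destinations, and section 9.9 lists adverse event collection and adhesion scoring as separate items with no link. One site might complete an adverse event form for each adhesion, another only for those it debrides, and a third for none. A single site may supply up to 60% of subjects (45 of 75), so its habit could dominate.

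The primary result is the rate of device-attributed or undetermined events with its confidence interval, and the study supports a CE Mark submission. If reporting followed local habit, that rate and the overall adverse event rate would depend partly on who enrolled the subjects. Adhesions could then appear under effectiveness and be missing from safety. The protocol does settle a similar overlap in section 11.2, for device deficiencies that cause an adverse event, so the lack of a matching sentence for adhesions stands out.

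**Working it through.** The documents state no figure to reproduce: SAP section 6 says that the minimum of 75 subjects has no statistical basis. The check is first a reading of the rules, then an illustration of size.

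**Reading the rules in order**

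1. *Is an adhesion an adverse event?* Table 9 covers untoward occurrences and clinical signs, anticipated or not and related or not. Protocol section 4.1.2 itself describes adhesions as unwanted and obstructive, and Appendix A lists them.
2. *Is it collected?* Section 11.1 says that all adverse event information is collected from surgery to the 30-day visit or exit.
3. *Is it exempt?* Table 8 has 13 entries. It covers 7 of the 9 inherent risks in section 10.1: mild bleeding, fatigue, moderate pain, inflammation and swelling, nasal congestion, headaches and facial pressure. Adhesions and infection are the two left out. The same 7 are Appendix A's normal expected complications, and adhesions are in its other list. An adhesion is therefore not exempt.
4. *Does it enter the primary count?* It does if it is attributed to the device or the cause cannot be determined (SAP section 7.9.1). Table 9 says that cases whose relatedness cannot be assessed are classed as possible, and both investigator and sponsor classify relatedness (Table 10). The list promised in section 11.4 is missing, but the protocol synopsis, section 13.3 and SAP section 7.9.1 all state the measure without that restriction. An analyst would use the unrestricted form.
5. *By visit or cumulative?* Scoring takes place at two visits, and section 13.4 names 2 weeks and 1 month. Tabulating by visit is the natural reading of SAP section 7.9.2.

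**Illustration of size**

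Assumptions, none from the documents except n = 75 and the 45-subject cap: k = 2 subjects with another device-attributed event; m = 15 other subjects (20%) with an adhesion; a = share of those 15 reported and attributed or undetermined; two-sided exact (Clopper-Pearson) 95% intervals. The protocol gives neither level nor method.

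Rate = (k + m × a) / 75

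| Case | Calculation | Rate (95% CI) |
|---|---|---|
| No adhesion counted | 2/75 | 2.7% (0.3 to 9.3) |
| a = 0.4 | (2 + 6)/75 | 10.7% (4.7 to 19.9) |
| Only a 45-subject site reports, all attributed | (2 + 0.20 × 45)/75 = 11/75 | 14.7% (7.6 to 24.7) |
| a = 1 | (2 + 15)/75 | 22.7% (13.8 to 33.8) |

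For m from 8 to 23 the rise is m × a / 75: at most 8/75 = 10.7 points to 23/75 = 30.7 points, and zero whenever a = 0.

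Two things follow. If every adhesion is reported, as steps 1 to 3 require, the full span from 2.7% to 22.7% is produced by causal attribution alone, and a rule about which form to complete would not narrow it. The part due to uneven reporting is the gap between the last two rows, (17 − 11)/75 = 8.0 points. It arises only if every other site ignores the default and every adhesion is attributed.

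**The case for a change.** The best case for a change is that the default has to be inferred. Debridement is a planned step at both visits, so a surgeon may see a small adhesion as an expected finding and only score it. Mild bleeding has the same double role, but Table 8 gives it a 5-day rule, and adhesions have none. There is no clinical events committee (section 12.1). Sponsor review under section 11.5.1 starts when an event is received, so it may not reach an adhesion that was scored and never entered. One sentence would settle the matter.

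Part of this stands. No text names adhesions in an adverse event instruction, and the cross-reference to section 11.4 leads nowhere. That empty reference affects every event type, however, and is not a defect in how adhesions are handled. A sentence would be tidier, but it would restate what the definition, the collection rule and Table 8 already imply. Section 9.2 sends sites to separate Case Report Form Instructions, which are not among the documents reviewed and may already cover the point. Monitoring checks that the events discussed in section 11 were reported (section 15.1).

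Going further would add little and could do harm. Limiting a cumulative adhesion measure to subjects scored at both visits would drop an adhesion seen at Day 14 in someone who missed Day 30, although SAP section 7.4 uses all observed data. Results by side, or tracking of re-formed adhesions, would need data that the protocol does not clearly collect.

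**Conclusion.** This is a missing detail that a competent team fills sensibly. Read as written, section 11 of the protocol makes an adhesion a reportable adverse event, and SAP section 7.9.1 counts it in the primary measure when it is attributed to the device or its cause is undetermined. Using the same observation as an effectiveness score is no contradiction. It also keeps adhesions visible in the report, because section 9.9 requires scoring at both visits whatever is entered on the adverse event form.

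The effect on the primary rate cannot be derived from the documents. Under the stated assumptions it lies between zero and 30.7 points, almost entirely according to attribution. The analyses are descriptive, with no hypothesis and no success threshold (protocol section 13.1, SAP section 6), so no pass or fail conclusion depends on it. The conclusion assumes that sites follow the general adverse event rule and that the form instructions do not contradict it. No change to the plan is needed.
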